7.1 Study Intervention/Device Description

Platelet-rich plasma kit it is defined as a device by the Food and Drug Administration (FDA).

7.2 Availability

Platelet-rich plasma kit and centrifuge machine is an investigational device supplied to investigators by Eclipse Medical.

7.3 Acquisition and Accountability

Agent Inventory Records/Device Logs – The investigator, or a responsible party designated by the investigator, will maintain a careful record of the inventory and disposition of all agents/device received from Eclipse Medical on a Drug Accountability Record Form (DARF) or Device Log.

7.4 Formulation, Appearance, Packaging, and Labeling

Platelet-rich plasma kit is a self-contained disposable kit containing two sterile blood separating vacuum tubes, two sleeve filters, various needles and a transferring device.

7.5 Product Storage and Stability

Sterile tubes and centrifuge machine should be stored in temperature between 41°F – 100°F. PRP should be applied to the same patient from whom the blood was drawn.

7.6 Preparation

Blood will be drawn from a vein in the patient's arm into a 11 ml Eclipse PRP Tube. The blood is processed using a centrifuge machine from eclipse medical. After centrifugation, the platelet poor portion will be separated from the platelet-rich portion.

7.7 Dosing and Administration

The proximal nail folds are cleansed with alcohol. Using a 1ml syringe and 30g needle, 0.1-0.2 ml of platelet-rich plasma is injected into 8 proximal nail folds (treated nails), while 2 proximal nail folds (untreated nails) are injected with platelet-poor plasma. The same volume will be administered during each study visit.

7.7.1 Dosing Delays/Dose Modifications

Table 2.

AGENT(S)	DOSE	ROUTE	VISIT
PRP, PPP	0.1-0.2 ml	Intramatricial	1
PRP, PPP	0.1-0.2 ml	Intramatricial	2
PRP, PPP	0.1-0.2 ml	Intramatricial	3

7.8 General Concomitant Medication and Supportive Care Guidelines

All concomitant medications will be recorded and/or updated on subject medication chart throughout the course of the study and saved in subject binder, if applicable.

7.9 Duration of Therapy and Criteria for Removal from Study

In the absence of treatment delays due to adverse event(s), treatment may continue for 3 cycles or until one of the following criteria applies:

- Intercurrent illness that prevents further administration of treatment,
- Unacceptable adverse event(s).
- · Subject decides to withdraw from the study, or
- General or specific changes in the subject's condition render the subject unacceptable for further treatment in the judgment of the investigator.

Study Termination Guidelines: A subject's follow-up in the study will end after one of the following applies:

- Subject's voluntary withdrawal
- Subject lost to follow-up
- Subject death
- Completion of all scheduled study follow-up appointments
- Any other rules specific to your study

7.10 Duration of Follow Up

Subjects will be followed 4 weeks after their last treatment. Subjects removed from study for unacceptable adverse events will be followed until resolution or stabilization of the adverse event.

7.11 Measures to Minimize Bias: Randomization and Blinding

Computer software will be used to randomly generate a randomization table. 8/10 fingernails will be randomly allocated to treatment with PRP and the remaining 2 fingernails will receive injections with PPP. Randomization for each participant will be done on the same day of their first treatment, after all inclusion and exclusion criteria, including a negative histopathology report for onychomycosis are fulfilled. For the present study, treatment will be open label with respect to patient and investigators but is blinded to the endpoint committee. High quality images will be obtained utilizing a Canon camera and reviewed by an independent blinded endpoint committee (3 dermatologists with expertise in nails disease [name], [name], and [name] [name]) for PGIA (Physician Global Improvement Assessment.

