1.2.2 Secondary Objectives

The secondary objective of this study is to demonstrate the safety and tolerability of PRP injections for brittle nails.

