3.3 Justification for Dose

The nail matrix, located at the proximal nail fold, functions as the nail growth center. We hypothesize that injecting 0.1-0.2 ml of platelet-rich plasma in this area will promote nail growth. On the other hand, injecting platelet-poor plasma, which lacks bioactive agents compared with the platelet-rich section, should not promote nail growth.

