4.4 Lifestyle Considerations

During this study, participants are asked to:

 Abstain from using any medication, moisturizers, oils, or nail polishes during the study period. Participants that do not fulfill this criterion will be excluded from the study.

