6.1.2 Treatment Phase

The 10 fingernails of each participant will be randomly assigned to treatment with platelet-rich plasma or platelet-poor plasma (placebo) treatment groups in a 8:2 ratio using a computer-generated randomization scheme developed by the data manager.

Study Visits Visit 1: Week 0 - 2

Subjects who fulfill all inclusion and exclusion criteria, and sign informed consent are eligible to enroll and begin Visit 1 procedures that same day. For those patients that do not have a negative histopathology result for onychomycosis within the past 6 months, a nail clipping is obtained during screening visit and visit 1 procedure will take place in week 2 assuming the patient fulfill all inclusion and exclusion criteria.

Visit 1 Procedures:

- Patient Instructions
- Take High resolution digital photographs
- Randomization of participants that fulfilled all inclusion and exclusion criteria
- First Injection of PRP

Visits 2 and 3: Week 4 - 6 (±7 days) and Week 8 - 10 (± 7 days) The following procedures will be performed on these visits:

Second and third injections of PRP

- Review of eligibility criteria including review of concomitant medications/cosmetics
- · Collection of adverse events
- Take High resolution digital photographs

Visit 4: Week 12 – 14 (± 7 days) Collection of adverse events

- Take High resolution digital photographs
- Collection of Patient Satisfaction Survey

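### Participants are left unmasked, with no reason given, although every nail gets a plasma injection; selective handling of known nails could alter the photographed outcome, and masking participants would be cheap

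*Combined protocol and SAP*

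**What the plan says.** On masking, Section 7.11 states that "treatment will be open label with respect to patient and investigators but is blinded to the endpoint committee". Section 1 (Protocol Summary), Section 3.1 and Section 3.2 describe the same PROBE design. None of them says why participants should not be masked.

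On the control, no nail is left uninjected. Under Section 7.7, eight nail folds receive PRP, while "2 proximal nail folds (untreated nails) are injected with platelet-poor plasma". Both fractions come from the same centrifuged blood (Sections 3.1 and 7.6), and Table 2 in Section 7.7.1 gives one volume range, one route and the same three visits for both. Section 6.1.2 describes allocation to "platelet-rich plasma or platelet-poor plasma (placebo) treatment groups in a 8:2 ratio". Section 3.3 expects the control to be inactive: "injecting platelet-poor plasma, which lacks bioactive agents compared with the platelet-rich section, should not promote nail growth".

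On nail care, Section 4.4 asks participants to "Abstain from using any medication, moisturizers, oils, or nail polishes during the study period", and says that those who do not comply will be excluded. Section 6.1.2 has concomitant medications and cosmetics reviewed at Visits 2 and 3.

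On outcomes, a blinded committee of three judges photographs after Visit 4 (Section 6.1.3). Section 12.1 compares follow-up with baseline within the PRP nails and, separately, within the others. Section 1.2.2 reads: "The secondary objective of this study is to demonstrate the safety and tolerability of PRP injections for brittle nails". Adverse events come from participants and staff (Section 13) and go into a log kept per participant (Section 13.1.3). A patient satisfaction survey is taken once, at Visit 4 (Table 1).

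**The concern.** The trial already carries the burden of a placebo injection: two nails at three visits, or 6 PPP injections per participant and 60 over 10 participants. One main return on that burden is that the recipient need not know which nail received what. An open-label design gives this up.

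Blinded reading protects the scoring of the photograph. It does not protect the nail before it is photographed. Over 12 to 14 weeks the participant decides how each nail is filed, trimmed and shielded from wear. Three of the five features named in Section 3.1 are forms of splitting, which such handling can plausibly affect. A participant who knows the two control fingers may favour the PRP nails, or may look after the PPP nails more to compensate. The resulting difference would be real and visible, so a blinded reader would score it correctly and still credit it to the wrong cause.

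At stake are the change from baseline in the PRP nails, which is the powered analysis, and any reading of that change against the PPP nails, which is what the control is there for.

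**Working it through.** **1. The plan's own figure, and whether masking changes it.** Inputs from Section 12.1: change 0.5, SD 1, paired two-sided t-test, alpha 0.05, power 90%. The normal approximation gives n = [(1.960 + 1.282) × 1 / 0.5]² = 42.0, so 43 nails. The exact noncentral t calculation gives 44, with power 0.900 at n = 44. The stated 44 reproduces. Masking participants changes none of these inputs, and the 80 PRP and 20 PPP nails in Section 12.2 stay as they are.

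**2. Is there already a sham to mask with?**

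| Feature | PRP nails | PPP nails | Source |
|---|---|---|---|
| Injected | 8 of 10 | 2 of 10 | 7.7 |
| Origin | same blood | same blood | 3.1, 7.6 |
| Volume range and route | 0.1-0.2 ml, intramatricial | same | Table 2, 7.7.1 |
| Visits | 1, 2, 3 | same | Table 2, 7.7.1 |
| Expected effect on growth | yes | no | 3.3 |

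So there is. The documents do not say whether the two fractions look different in a syringe.

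**3. Which routes to bias stay open?**

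- *Products:* restricted for all nails by Section 4.4 and reviewed under Section 6.1.2. Largely closed.
- *Filing, trimming, protecting:* not mentioned anywhere. Open.
- *Reports of local symptoms:* Sections 2.4.1 and 13.1.1 list pain and tenderness among the expected events. However, the log is per participant, and the event fields in Section 13.4 include neither nail nor arm. Open only if events are later attributed to a finger.
- *Survey:* not specified per nail and analysed descriptively.

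**4. Scale, under assumptions that are not in the documents.** Suppose the PRP and PPP nails were compared by taking, for each of 10 participants, the mean change of 8 PRP nails minus the mean change of 2 PPP nails. Take SD 1 per nail change and within-person correlation ρ. Then SE = √[(1 − ρ)(1/8 + 1/2)/10]. A spurious difference b enters a two-sided t-test on 9 df with noncentrality b/SE. The false-positive rate, nominally 5%, becomes:

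| ρ | SE | b = 0.1 | b = 0.2 | b = 0.3 |
|---|---|---|---|---|
| 0 | 0.250 | 6.5% | 11.1% | 18.9% |
| 0.3 | 0.209 | 7.1% | 13.8% | 25.0% |
| 0.5 | 0.177 | 8.0% | 17.4% | 32.9% |
| 0.7 | 0.137 | 10.0% | 25.8% | 49.8% |

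This shows only how sensitive such a comparison would be. Nothing in the documents fixes b, and Section 12.1 does not specify this test.

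**5. Would covering the syringes be enough?** Eight nails at 0.1-0.2 ml need 0.8-1.6 ml of PRP per visit. With the 1 ml syringe of Section 7.7, that is one or two syringes if shared across nails, with PPP in another. A participant who watches would see which two fingers call for a different syringe. Sleeves hide colour, not the change of syringe; one syringe per finger hides both.

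**The case against.** PROBE is a declared design, stated consistently, and it blinds the scoring of the primary endpoint. The product ban covers all nails and is checked. The documents offer no evidence that participants would file or protect particular fingers selectively, and they describe no procedure for disclosing the allocation; that participants know it is inferred from the open-label wording. All of this is fair, and it reduces the point to a limited route of bias.

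The planned tests are within-arm, so a bias between arms does not enter a specified test of PRP against PPP. This also stands. Preferential care of PRP nails would still inflate the within-PRP change directly. Masking would not remove changes that affect all nails alike, such as stopping polish, from a comparison with baseline.

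Two stronger readings are tempting, and the documents support neither:

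- *A size for the bias.* A reader might suppose that one feature changes in 10-20% of the nails of one arm, obtain 0.1-0.2 points, and call this 20-40% of the planned 0.5. The 10-20% is invented. The arithmetic also counts points on the five-feature PGA, while Sections 1.2.4 and 12.1 name the PGIA as primary and no point scale is given for it. Section 10 says the committee assesses change on the PGA, but that inconsistency does not settle a scale. The 0.5, moreover, is a within-PRP change and not a difference between arms.
- *Biased safety results by arm.* A reader might infer that pain and tenderness will be reported differently for PRP and PPP nails. No analysis by nail is planned, and neither the log nor the survey is specified by nail.

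**Conclusion.** The point holds as a cheap improvement. Participants are unmasked although a sham injection is already in place, and the documents state neither a benefit of open labelling nor an obstacle to masking. One route stays open that blinded reading cannot correct: unequal filing, trimming or protection of nails whose allocation is known. It could inflate the within-PRP change, or distort a reading of PRP against PPP nails in either direction.

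The size cannot be estimated from the documents. The conclusion assumes that open label means participants know, or can see, which nails receive which fraction, and that some of them would act on it. The local-symptom argument counts only if events are attributed to a nail. To say that open labelling brings no benefit at all would be a judgement; the documents show only that none is stated.

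**What to change.** - In Sections 1, 3.1, 3.2 and 7.11, state that participants are not told which nails receive PRP and which PPP. The committee stays blinded as now.
- At each treatment visit, prepare ten identical opaque-sleeved syringes out of the participant's view, labelled by finger, so that neither colour nor a change of syringe reveals the allocation.
- Use the same wording to the participant for every nail, and stop calling the PPP nails untreated (Sections 3.1 and 7.7); this also brings the text into line with Section 6.1.2.
- At Visit 4, ask each participant to guess the allocation of each nail, and report the result.

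Existing investigators may stay unmasked, so no extra staff are needed. Randomization, nail counts and the sample-size calculation are untouched.

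Cost: if PRP would otherwise come from one or two shared syringes and PPP from one, ten per visit means seven or eight more. Add some preparation time and rewording of the consent form. Masking may be imperfect. The Visit 4 guess measures that but does not prevent it, and imperfect masking is no worse than the present open design.

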7.12 Study Intervention/Follow-up Compliance

During the baseline visit (standard of care visit), participants will be asked to schedule their follow-up study visits. In addition, patients will receive a call prior to their scheduled visit in order to confirm attendance.

8. Study Intervention Discontinuation and Participant Discontinuation/Withdrawal

Participants may withdraw voluntarily from the study or the PI may discontinue a participant from the study. Participants will be excluded if they have/develop psoriasis, lichen planus, dermatophyte infection or other confounding abnormalities that are severe enough to result in a clinically abnormal fingernail. Have used any medication within 90 days prior to the start of the study. Use of nail polishes or gels during the study period. The subject gets pregnant or is planning pregnancy.

8.1 Discontinuation of Study Intervention

Discontinuation from PRP does not mean discontinuation from the study, and remaining study procedures should be completed as indicated by the study protocol. If a clinically significant finding is identified (including, but not limited to changes from baseline) after enrollment, the investigator or qualified designee will determine if any change in participant management is needed. Any new clinically relevant finding will be reported as an adverse event (AE).

The data to be collected at the time of study intervention discontinuation will include the following:

 Reason(s) for discontinuation, take digital photographs, assessment of concomitant medications.

8.2 Participant Discontinuation/Withdrawal from the Study

Participants are free to withdraw from participation in the study at any time upon request. An investigator may discontinue or withdraw a participant from the study for the following reasons:

- Pregnancy
- Significant study intervention non-compliance
- If any clinical adverse event (AE), laboratory abnormality, or other medical condition or situation occurs such that continued participation in the study would not be in the best interest of the participant
- If the participant meets an exclusion criterion (either newly developed or not previously recognized) that precludes further study participation
- Participant unable to receive PRP.
- Participant lost to follow-up after several attempts to contact subject to schedule study visit.

The reason for participant discontinuation or withdrawal from the study will be recorded on the Case Report Form (CRF). Subjects who sign the informed consent form and are randomized but do not receive the study intervention may be replaced. Subjects who sign the informed consent form, and are randomized and receive the study intervention, and subsequently withdraw, or are withdrawn or discontinued from the study, will be replaced.

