12.6.2 Evaluation of Response

All subjects included in the study will be assessed for response to treatment if they have received at least 3 treatments.

13. Adverse Event Reporting Requirements

Adverse event (AE) monitoring and reporting is a routine part of every clinical trial. The investigator will be required to provide appropriate information concerning any findings that suggest significant hazards, contraindications, side effects, or precautions pertinent to the safe use of the drug or device under investigation. Safety will be monitored by evaluation of adverse events reported by subjects or observed by investigators or research staff, as well as by other investigations such as clinical laboratory tests, x-rays, electrocardiographs, etc.

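### Section 12.6.2 assesses response only after all three injections, so the primary test in PRP nails is a treatment-completer analysis; the likely bias is small and the remedy is wording

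*Combined protocol and SAP*

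**What the plan says.** Section 12.6.2 defines who is assessed for efficacy: "All subjects included in the study will be assessed for response to treatment if they have received at least 3 treatments". Three is also the maximum. Section 7.9 says "treatment may continue for 3 cycles or until one of the following criteria applies", and the dosing table in 7.7.1 lists visits 1, 2 and 3 only.

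Two sections deal with early stopping. Section 8.1 separates stopping treatment from leaving the study: "Discontinuation from PRP does not mean discontinuation from the study, and remaining study procedures should be completed as indicated by the study protocol". The data it collects at that point begin with "Reason(s) for discontinuation, take digital photographs". Section 8.2 lists grounds on which the investigator may withdraw a participant. One begins "If any clinical adverse event (AE), laboratory abnormality, or other medical condition or situation occurs such that continued participation" and turns on what is best for the participant; another is "Participant unable to receive PRP". Those who have been randomised "and receive the study intervention, and subsequently withdraw, or are withdrawn or discontinued from the study, will be replaced". No ground for leaving is exempt from replacement, and the section does not say whether a replacement's data join or displace those of the person replaced.

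Section 7.10 covers removal for toxicity: "Subjects removed from study for unacceptable adverse events will be followed until resolution or stabilization of the adverse event". That is follow-up of the event, not of efficacy. Section 12.6.1 keeps everyone in the toxicity evaluation from the first injection. Section 12.1 plans the primary comparison as weeks 12-14 against baseline within PRP nails, and separately within nails without PRP. Section 12 names no all-treated analysis, missing-data method or sensitivity analysis.

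**The concern.** Membership of the response set depends on something that happens after randomisation and may be related to outcome: whether the participant tolerated and received all three injections. Section 13.1.1 lists pain, scarring, bleeding and infection at the injection site among the expected events, and section 2.4.1 says PRP has not been studied in nail disease, so stopping for a local reaction is plausible. That participant's eight PRP nails would then be missing from the primary test, although section 8.1 keeps the participant in the study and under the camera.

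The planned test has no built-in protection. Randomisation is of nails within a person, so PRP and PPP nails leave together, and a PRP-minus-PPP contrast would be affected less. Section 12.1 plans none; it compares PRP nails with their own baseline. With 10 participants, one person is a tenth of the data. At stake is whether the reported mean change describes everyone who started PRP or only those who finished it.

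**Working it through.** **The plan's own figure.** For a paired two-sided t-test at 0.05 with 90% power, a change of 0.5 and SD 1, exact noncentral-t calculation gives 44 nails, as section 12.1 states. The other five cells of its table also reproduce (5, 13, 26 for a difference of 1; 13 and 97 for 0.5). At the planned 80 PRP nails, treated as independent as the plan does, power is 99.3%. The sample-size arithmetic is not in dispute; the point concerns the analysis set.

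**The rules side by side.**

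| Participant | Assessed for response (12.6.2)? | Replaced (8.2)? |
|---|---|---|
| Three injections, completes Visit 4 | Yes | No |
| Stops PRP early, stays under 8.1 | No, by implication | Not clearly |
| Leaves the study before the third injection | No, by implication | Yes |
| Leaves after the third injection, before Visit 4 | Yes | Yes; not resolved |

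**Size for one affected participant.** From the documents: 10 participants, 8 PRP nails each, 80 in all; target change 0.5; SD 1. Assumed: completers' nails improve by 0.5; one participant stops early with one PRP nail worse by 1 point; that person's other 7 PRP nails change by *c*.

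Mean if kept = (72 × 0.5 + 7*c* − 1) / 80. The completer mean is 0.500.

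| *c* | Mean if kept | Shift | Share of 0.5 |
|---|---|---|---|
| 0.5 (full improvement) | 0.481 | 0.019 | 4% |
| 1/3 (2 of 3 injections, pro rata) | 0.467 | 0.033 | 7% |
| 1/6 (1 of 3 injections, pro rata) | 0.452 | 0.048 | 10% |
| 0 (no improvement) | 0.438 | 0.063 | 12.5% |

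Two such participants double each shift.

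**Which rule produces the shift?** Take *c* = 0.5.

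- Left out, not replaced: 72 × 0.5 / 72 = 0.500.
- Left out, replaced by a completer: 80 × 0.5 / 80 = 0.500.
- Kept, no replacement: 0.481.
- Kept, replacement added: (80 × 0.5 + 7 × 0.5 − 1) / 88 = 42.5 / 88 = 0.483.

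The move from about 0.48 to 0.50 comes from the three-treatment rule. Replacement changes the mean by 0.002 at most.

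**Against sampling error.** With 80 independent nails, SE = 1/√80 = 0.112, so 0.019 is 0.17 SE and 0.063 is 0.56 SE. Nails within a person are unlikely to be independent. With an assumed within-person correlation ρ, SE = √[(1 + 7ρ)/80], which is 0.197 at ρ = 0.3 and 0.272 at ρ = 0.7. The shifts are then 0.07 to 0.10 SE and 0.23 to 0.32 SE.

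**How often.** The documents give no rate. If the chance of such a stop is *p* per participant, the chance of at least one in 10 is 1 − (1 − *p*)^10: 18%, 40% or 65% for *p* = 2%, 5% or 10%.

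**The case against.** The strongest defence is that a per-protocol response set is a reasonable choice for a 10-person study of a three-injection course. It is stated openly, and every treated participant is kept for safety. Section 12.6.2 does not expressly bar rating someone with fewer injections, and the expected events are described as mostly mild and transient, although from hair and skin use. Many reasons for leaving (pregnancy, loss to follow-up, intercurrent illness) need have nothing to do with how the nails respond. All of this stands, and it limits the weight of the point. It does not explain why photographs of a participant retained under 8.1 should have no place in any planned efficacy analysis.

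It is also fair that a discontinuation photograph may be taken well before weeks 12-14. Putting it in the primary analysis would mix time points, so the fix keeps it out.

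A reader might go further in two ways that the documents do not support. First, one might see replacement under 8.2 as the source of bias; the arithmetic shows it is not. Second, one might read the exclusion in section 8 for newly developed nail abnormalities, or the medication ban in 4.4, as removing people with injection-site infection or scarring. The natural meaning of the first is other nail disease, as in the exclusion criteria. The second, read with 3.1 and 7.8, most likely means products used on the nails. Nothing here rests on either, or on section 8 being worded more firmly than 8.2.

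**Conclusion.** The point holds as a modest one. Sections 7.9 and 12.6.2 together make the primary result a treatment-completer analysis, no all-treated analysis is planned, and section 8.1 does not repair this because it retains the participant without making that person assessable.

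The direction is conditional. The result favours PRP only if early stopping is linked to harm or poor response. Neither 7.9 nor 8.2 names lack of response or worsening brittleness as a ground for stopping, so it would be wrong to infer that the plan systematically discards failures. In an extreme simulation with no true effect, in which the worst-responding participants are the ones replaced, a participant-level t-test rejects about 10% of the time with one replacement and 19% with two, against a nominal 5%. That is an upper bound, not a forecast.

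Under the stated assumptions the shift is 0.019 to 0.063 points per affected participant, or 4% to 12.5% of the 0.5 target. The stopping rate, the one-point worsening and the values of *c* are all assumptions. The likely effect is small; the case for change is that the remedy is cheap.

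**What to change.** 1. **Section 12.6.2.** Define the primary response set as all nails of every treated participant with a Visit 4 (week 12-14) photograph, whatever the number of injections. Report the three-treatment set as a sensitivity analysis.
2. **Treated participants with no Visit 4 photograph.** Use the discontinuation photograph that 8.1 already requires, in a second sensitivity analysis only. This also settles the case of someone who leaves between the third injection and Visit 4: outside the primary set, and in this analysis if a photograph was taken.
3. **Section 8.2.** State that a replacement's data are added to, and never substituted for, those of a treated participant. This mainly protects the second sensitivity analysis, since someone who leaves the study will usually have no Visit 4 photograph.

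The changes should be made before the committee's scores are seen. They need wording in two sections and two short extra analyses. No new visits or images are needed, because photographs at every visit and at discontinuation are already planned. The downside is that partly treated participants dilute the estimate slightly; comparison with the three-treatment set will show by how much.
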